## **PRÉCIS**

## **Background:**

- Hairy cell leukemia (HCL) is an indolent CD22+ B-cell leukemia comprising 2% of all leukemias, or approximately 1200 of the 62,130 new cases of leukemia/year in the US. HCL variant (HCLv), also CD22+, is 10-20% as common as HCL, but more common in the relapsed/refractory population due to its poor prognosis and response to standard purine analog chemotherapy. HCLv cells are CD25-negative and wild type for BRAF, so HCLv patients are not candidates for BRAF inhibitors. CD25+ classic-appearing HCL-cells that express unmutated IGHV4-34 are wild-type for BRAF, remain brightly CD22 positive, and confer a poor prognosis when treated with chemotherapy.
- Moxetumomab pasudotox-tdfk is a recombinant immunotoxin containing a variable domain (Fv) fragment of an anti-CD22 monoclonal antibody and truncated Pseudomonas exotoxin, which kills CD22+ cells by binding to CD22 via the Fv fragment, and induction of apoptotic cell death catalytic inhibition of protein synthesis in the cytosol.
- Moxetumomab pasudotox-tdfk in phase 1 testing demonstrated a high complete response (CR) rate in patients with chemoresistant HCL, without dose-limiting toxicity (DLT), but with reversible grade 2 hemolytic uremic syndrome (HUS) not requiring plasmapheresis.
- Moxetumomab pasudotox-tdfk completed multicenter phase 3 testing in 80 patients, meeting its CR endpoint, with 8.8% incidence each of capillary leak syndrome (CLS, grade 3-4 2.5%), and HUS (grade 3-4 6.3%), both reversible.
- Moxetumomab pasudotox-tdfk is the only known non-chemotherapy-containing regimen for HCL which can consistently eradicate minimal residual disease (MRD), and this is associated with prolonged CR durations. Recently, US Food and Drug Administration (FDA) has accepted the Biologics License Application (BLA) for moxetumomab pasudotox-tdfk as the treatment of adult patients with HCL.
- Patients who did not achieve CR, or CR with MRD, often made neutralizing antibodies to the bacterial-based toxin, and/or had collections of HCL cells not completely eradicated by moxetumomab pasudotox-tdfk. Both issues may be addressed by the addition of anti-CD20 monoclonal antibody (Mab) rituximab or Ruxience to Moxetumomab pasudotox-tdfk.

# **Objective:**

• To determine the safety and toxicity of Moxetumomab pasudotox-tdfk and rituximab/Ruxience used at the planned dose level, in participants with HCL and HCLv.

## **Eligibility:**

- HCL or HCLv with at least 1 prior purine analog, and, for HCL participants with ≥2-years 1 month response, at least 1 other therapy.
- Need for treatment, either 1) ANC <1/nL, 2) Hgb <10g/dL, 3) Plt <100/nL, 4) symptomatic splenomegaly, or enlarging HCL mass > 2cm in short axis
- Serum creatinine < 1.5 mg/dL, or creatinine clearance  $\geq$  60 mL/min by Cockcroft-Gault equation, where creatinine clearance = (140-age)(kg weight)/(72 x Creatinine).
- No uncontrolled infection or cardiopulmonary dysfunction

Version Date: 04/16/2025

## Design:

• Phase I trial, two arm, non-randomized, dose escalation

#### • Administration:

- O Participants 1-13: Moxetumomab pasudotox-tdfk 30-40 mcg/kg intravenous (iv) over 30 min, rituximab 375 mg/m² iv, 50-400 mg/hr.
- o Participants 14-26: Moxetumomab pasudotox-tdfk 40 mcg/kg intravenous (iv) over 30 min, Ruxience 375 mg/m² iv, 50-400 mg/hr
- Rituximab or Ruxience day 1 (begin day -2 on cycle 1), Moxetumomab pasudotox-tdfk days 1, 3, and 5.
- Participants will receive up to 4 cycles past documentation of CR without MRD, maximum
   8.
- o To prevent renal toxicity and hypovolemia, participants will be encouraged to drink water gradually, approximately 1 cup/hour or 6L/day, not going >3 hours without drinking from days 1 to 8 and to keep a hydration diary to record daily fluid consumption.
- o To prevent rituximab/Ruxience toxicity, participants will receive prophylactic dexamethasone orally 0.5-2 hours before the 1st dose of rituximab/Ruxience, and before subsequent doses until rituximab/Ruxience infusion reactions are not seen. Participants will also receive diphenhydramine, famotidine and acetaminophen.
- O Dexamethasone 4 mg orally (maximum 2 doses/day) will be given as needed to treat nausea or fever associated with Moxetumomab pasudotox-tdfk, which might prevent adequate water intake

## • Statistical design:

 Up to 26 participants are intended to be treated in the trial. While a total of 26 evaluable participants will be enrolled, the accrual ceiling will be set at 30 to include screen failures and inevaluable participants.

Version Date: 04/16/2025

#### STATEMENT OF COMPLIANCE

The trial will be carried out in accordance with International Council for Harmonisation Good Clinical Practice (ICH GCP) and the following:

• United States (US) Code of Federal Regulations (CFR) applicable to clinical studies (45 CFR Part 46, 21 CFR Part 50, 21 CFR Part 56, 21 CFR Part 312, and/or 21 CFR Part 812)

National Institutes of Health (NIH)-funded investigators and clinical trial site staff who are responsible for the conduct, management, or oversight of NIH-funded clinical trials have completed Human Subjects Protection and ICH GCP Training.

The protocol, informed consent form(s), recruitment materials, and all participant materials will be submitted to the Institutional Review Board (IRB) for review and approval. Approval of both the protocol and the consent form must be obtained before any participant is enrolled. Any amendment to the protocol will require review and approval by the IRB before the changes are implemented to the study. In addition, all changes to the consent form will be IRB-approved; an IRB determination will be made regarding whether a new consent needs to be obtained from participants who provided consent, using a previously approved consent form.

#### 1 INTRODUCTION

## 1.1 STUDY OBJECTIVES

## 1.1.1 Primary Objective

To determine the safety and toxicity of moxetumomab pasudotox-tdfk and rituximab/Ruxience treated at the planned dose level, in participants with HCL and HCLv.

## 1.1.2 Secondary Objectives

- To determine the minimal residual disease (MRD)-free CR rate of the study drug combination is higher than that achieved with 40-50 mcg/kg dose levels of Moxetumomab pasudotox-tdfk alone.
- To determine response rates and duration of response.

## 1.1.3 Exploratory Objectives

- To determine the incidence of anti-moxetumomab antibodies after combined treatment.
- To determine the plasma levels of moxetumomab pasudotox-tdfk with combined treatment.
- To determine the effects of combined therapy on normal B and T-cells.

## 1.2 BACKGROUND AND RATIONALE

## 1.2.1 Background

Hairy cell leukemia (HCL) is an indolent CD22+ B-cell leukemia comprising 2% of all leukemias [1, 2], or approximately 1200 of the 62,130 new cases of leukemia/year in the US [3]. HCL variant (HCLv), also CD22+, is 10-20% as common as HCL, but more common in the relapsed/refractory

Version Date: 04/16/2025

population due to its poor prognosis and response to standard purine analog chemotherapy [4, 5]. HCLv cells are CD25-negative and wild type for BRAF, so HCLv patients are not candidates for BRAF inhibitors [6]. CD25+ classic-appearing HCL-cells that express unmutated IGHV4-34 are wild-type for BRAF, remain brightly CD22 positive, and confer a poor prognosis when treated with chemotherapy [7].

Moxetumomab pasudotox-tdfk is an anti-CD22 recombinant immunotoxin reported in the dose-escalation part of a phase I trial to achieve 46% complete remission (CR) and 86% overall response (ORR) rates, without dose-limiting toxicity (DLT) [8]. Two patients had completely reversible grade 2 hemolytic uremic syndrome (HUS), but no chemotherapy-type myelosuppressive or cumulative toxicities were observed.

Long-term follow-up of these 28 patients, including 12 who received the upper dose 50 mcg/kg every other day for 3 doses (QODx3), and an extension cohort of 21 patients receiving this dose, documented a CR rate of 64% in the 33 patients receiving 50 mcg/kg QODx3. Moreover, of 32 patients evaluated for minimal residual disease (MRD) with bone marrow biopsy (BMBx) immunohistochemistry (IHC) and flow cytometry of blood and bone marrow aspirate (BMA), 11 (34%) were MRD-negative. Median CR duration was not reached (up to 72 months) in those MRD-negative vs 13.5 months in those MRD+ (p<0.0001). Of the 3 tests for MRD, the most sensitive by far was BMA flow cytometry, and patients MRD+ by this study were sometimes positive by blood flow cytometry, IHC, or both [9]. Multicolor high sensitivity flow cytometry was used for both blood and BMA, and results read as suspicious are considered negative. MRD+ by IHC of BMBx requires at least as many B as T-cells, and for most of the B-cells to be consistent with HCL [10]. As exploratory endpoints, MRD is also determined by PCR, using consensus primers to a variable framework domain (FR1, FR2 or FR3), and a junctional or constant domain (JH or CH) of the immunoglobulin heavy chain rearrangement (IgH) [11, 12]. This assay, performed in the Molecular Pathology Section of the Laboratory of Pathology, NCI, is considered positive if the band corresponding to the HCL IgH can be recognized over a background of IgH bands from normal B-cells. Lack of normal B-cells, either due to HCL, chemotherapy or rituximab, may allow the HCL IgH band to more easily be seen. A research PCR assay is also done in the [name] Lab using patient- specific primers with a probe [11]. This patient- or clone-specific assay can detect 1 HCL in 10^6 normal cells but requires a different PCR assay for each patient.

Of 32 patients at 50 mcg/kg QOD x3 evaluated for neutralizing (antidrug) antibodies, 24 (75%) had >50% neutralization of 200 ng/ml, and 17 (53%) had >75% neutralization of 1000 ng/ml of moxetumomab pasudotox-tdfk. Since CR duration was higher with compared to without consolidation cycles of moxetumomab pasudotox-tdfk (p=0.0004), and since early immunogenicity prevented consolidation cycles, prevention of immunogenicity is an important goal in immunotoxin treatment of HCL [9]. Further analysis of response vs immunogenicity, reported in the supplemental section of phase I report [9], showed trends for higher MRD-negative CR rate (8 of 15 vs. 3 of 17; P = .06) and longer CR duration (median undefined vs. 19.1 months, P = .05) in patients without vs. with antibodies neutralizing more than 75% of the activity of 1000 ng/ml of moxetumomab pasudotox-tdfk. Pharmacokinetic analysis in this report showed that despite early neutralizing antibodies which made patients ineligible for future cycles (>50% neutralization of 200 ng/ml), we could observe increases in peak level and area under curve (AUC), and decreases in volume of distribution and clearance, from the 1st dose to the 3rd dose of the last cycle. This indicated that even secondary immunogenicity with moxetumomab pasudotox-tdfk in

Version Date: 04/16/2025

HCL was too weak to prevent titration of antidrug antibodies by repeated dosing. This make it possible that an agent like rituximab, which could not prevent immunogenicity in solid tumors [13] receiving a large immunotoxin chemical conjugate, may prevent it in HCL patients with impaired immune system receiving a smaller recombinant immunotoxin.

A phase 3 pivotal multicenter single-arm trial (NCT01829711) was designed for relapsed/refractory HCL patients with ≥2 prior systemic therapies including ≥1 prior purine analog. Patients received moxetumomab pasudotox-tdfk 40 mcg/kg intravenously on days 1, 3, and 5 of each 28-day cycle for 6 cycles, or until MRD-negative CR, disease progression, initiation of alternate therapy, or unacceptable toxicity. Disease response and immunohistochemistry MRD status were determined by blinded independent central review. The primary endpoint was durable CR, which required achieving CR and maintaining hematologic remission (HR) for >180 days). HR was defined as hemoglobin >11.0 g/dL, absolute neutrophil count >1.5/nL, and platelet count ≥100/nL without transfusions or growth factors within the preceding 4 weeks of assessments. Eighty patients (63 males, 17 females; median age 60 years (range 34-84) were enrolled. The median number of previous systemic therapies was 3 (2–11); 48.8% of patients were purine analog refractory and 37.5% were unfit for purine analog retreatment. The median number of treatment cycles administered was 6 (1-7). As of May 24, 2017, the durable CR rate was 30.0%, 24/80 patients; 95% confidence interval (CI): 20.3, 41.3). CR rate was 41.3% (33/80 patients; 95% CI: 30.4, 52.8), and ORR was 75% (95% CI: 64.1, 84.0). Among 33 patients who achieved a CR, 27 (81.8%) also achieved MRD negativity. Median time to OR was 5.7 months (95% CI: 5.7, 5.9). Sixty-four patients (80%) achieved hematologic remission. The median duration of hematologic remission from CR, median duration of response, and PFS were not reached.

Of 64 patients treated on the phase 1 (NCT01087333) and 3 (NCT01829711) trials at NIH with 40-50 mcg/kg dose levels of moxetumomab pasudotox-tdfk and evaluated for MRD by bone marrow aspirate flow cytometry, the 30 (47%) of 64 achieved MRD-free CR.

The most frequently reported adverse events (AEs) occurring in >40% of subjects overall were hypoalbuminemia (71.4%), increased ALT (67.3%); increased AST (63.3%), lymphopenia (59.2%), myalgia (57.1%); decreased white blood cell count (51.0%); pyrexia (49.0%); peripheral edema (44.9%); and hypertriglyceridemia (40.8%).

A total of 48 phase I subjects (98%) had AEs that were assessed by the investigator as related (possibly, probably, or definitely) to investigational product. The most frequent treatment-related AEs occurring in > 20% of subjects were hypoalbuminemia (69.4%), increased ALT (63.3%), increased AST (61.2%), peripheral edema (42.9%), pyrexia (42.9%), myalgia (40.8%), headache (36.7%), nausea (32.7%), fatigue (28.6%), edema (24.5%), hypotension (24.5%), and chills (22.4%). Treatment-related grade 3/4 AEs were reported in 30.0% of patients. Three deaths were reported (due to pneumonia, sepsis, and sepsis syndrome); none were considered treatment-related by the investigators. Treatment-related AEs that most frequently led to permanent discontinuation were hemolytic uremic syndrome (HUS), capillary leak syndrome (CLS), and blood creatinine increased, reported in 4 (5.0%), 2 (2.5%), and 2 (2.5%) patients, respectively. Seven patients (8.8%) had CLS (grade 2: n=5; grade 4: n=2), 7 patients (8.8%) had HUS (grade 2: n=2; grade 3: n=3; grade 4: n=2), and 4 patients (5.0%) had both CLS and HUS. In general, CLS and HUS events were manageable and reversible with appropriate supportive care, monitoring, and, in severe events, treatment discontinuation. Grade 3-4 AEs, regardless of attribution, occurring in at least 2.5% of patients included lymphopenia (20%), hypophosphatemia or anemia (10%), leukopenia

Version Date: 04/16/2025

(8.8%), hypertension, (7.5%), thrombocytopenia or neutropenia (6.3%), HUS, febrile neutropenia, or neutropenia (5%), and nausea, hypokalemia, hyponatremia, CLS, upper respiratory infection, hypoxia, lung infection, acute kidney injury, or erysipelas (2.5%). A number of eye changes have been reported in studies with moxetumomab pasudotox-tdfk; serious events including inflammation of the nerve for sight and retinal detachment have occurred in the acute lymphoblastic leukemia [14].

In this study, anti-drug antibodies were detected at baseline in 45/76 evaluable patients (59.2%). The frequency of neutralizing antibodies and anti-drug antibody titer increased with repeated cycles of treatment; reduced drug exposure was observed in patients with high-titer (>10,000) anti-drug antibodies. Patients who achieved complete or partial response typically maintained antibody titers below 10,000 and therefore maintained drug exposure for more treatment cycles than patients with stable or progressive disease, suggesting that approaches to reduce the immunogenicity of moxetumomab pasudotox-tdfk might further improve response.

In the phase 3 trial, 70 (87.5%) patients received prior rituximab, and although we do not have extramural data regarding whether rituximab was used close to the time prior to enrollment, we do know that 2 of our patients received rituximab within 6 months prior to enrollment and therefore likely had positive rituximab levels during administration of moxetumomab pasudotox-tdfk. One patient had a transient HUS-like event, and one did not, both patients achieving MRD-negative CR.

In summary, moxetumomab pasudotox-tdfk achieved a high rate of independently assessed, deep, and durable response, with ability to eradicate bone marrow MRD in heavily pretreated patients with HCL, and had a favorable safety profile, manageable and reversible CLS/HUS, and no associated myelo/immunosuppression. Both phase 1 and 3 data suggest its efficacy could be improved with addition of rituximab. Recently, US Food and Drug Administration (FDA) has accepted the Biologics License Application (BLA) for moxetumomab pasudotox-tdfk as the treatment of adult patients with HCL.

Rituximab is a genetically engineered chimeric mouse/human IgG1 anti-CD20 monoclonal antibody (mAb) approved for the treatment of non-Hodgkin's lymphoma, chronic lymphocytic leukemia, and moderate-to-severe rheumatoid arthritis [15]. Rituximab binds to CD20 on the surface of B cells and elicits a signaling cascade resulting in cell death. It also enhances antibody dependent and complement dependent cellular toxicity. Treatment with rituximab causes depletion of CD20+ B cells in peripheral blood and tissues, thereby reducing antigen presentation and activation of T cells, autoantibody production, and cytokine production [16, 17]. Rituximab has modest single-agent activity in relapsed HCL requiring treatment due to cytopenias, with CR rate 13% and ORR 25% [18]. Rituximab has been used extensively at NCI for the treatment of HCL on two investigator sponsored trials (IST), either concurrently with the purine analogs cladribine, pentostatin or bendamustine, or in delayed fashion as a single agent for MRD clearance after cladribine. Rituximab reliably decreases circulating normal B-cells to undetectable levels for at least 6 months after the last dose. This decrease was not sufficient to block the immunogenicity of the highly immunogenic immunotoxin chemical conjugate LMB-1 in patients with solid tumors [13], but may be sufficient to block immunogenicity of the smaller recombinant immunotoxin moxetumomab pasudotox-tdfk in patients with HCL who have already compromised B-cell function and numbers.

However, access to rituximab is limited by factors such as availability, reimbursement, and

Version Date: 04/16/2025

insurance coverage. Moreover, patent portfolios for rituximab have expired or are nearing the end of term, which, in turn, has prompted the development of biosimilars [19]. Rituximab biosimilars are approved by the US Food and Drug Administration (FDA) (https://www.fda.gov/drugs/fdaapproves-truxima-biosimilar-rituxan-non-hodgkins-lymphoma). Ruxience was recently approved by the FDA for the treatment of non-Hodgkin's lymphoma (NHL), chronic lymphocytic leukemia granulomatosis with polyangiitis and microscopic polyangiitis (CLL), and (https://www.accessdata.fda.gov/drugsatfda\_docs/label/2019/761103s000lbl.pdf). Ruxience has the same primary amino acid sequence as rituximab reference products [20]. Moreover, comparative studies have shown similar structural, functional, and animal toxicity profiles of Ruxience and rituximab [20]. Pharmacokinetic (PK) bioequivalence between Ruxience and rituximab-US has been demonstrated in subjects with rheumatoid arthritis [21].

Ruxience has been shown in several clinical trials to be equivalent to rituximab, including in a recent trial for follicular lymphoma in which similar CD19-positive B-cell depletion, safety, and immunogenicity between all treatment groups was demonstrated [22].

#### 1.2.2 Rationale

Moxetumomab pasudotox-tdfk is the only known non-chemotherapy agent capable of eliminating HCL MRD in a high percentage of patients with relapse HCL, and in this patient population, elimination of MRD significantly prolongs CR duration. Of 11 participants on the phase I trial without MRD after 50 mcg/kg QODx3 of moxetumomab pasudotox-tdfk, 9 remained without MRD at 24-69 (median 42) months, suggesting that cure of this disease may be possible without chemotherapy.

Optimization of the effectiveness of moxetumomab pasudotox-tdfk, through combination with rituximab/Ruxience, may lead to more rapid and complete removal of tumor bulk and more effective tumor cell targeting of the immunotoxin, and at the same time, a decrease in immunogenicity through the action of both agents on normal B-cells.

Avoidance of chemotherapy in the treatment of HCL may prevent long term and permanent damage to stem cells and CD4+ T-cell numbers, which might, to some extent, prevent opportunistic infections and secondary malignancies. In addition, purine analog chemotherapy is associated with cumulative neurotoxicity and myelodysplastic syndrome. Except in extremely rare cases, toxicity due to rituximab/Ruxience is limited to infusion reactions which can be mostly prevented by steroids and generally resolve after the 1st or 2nd of 8 weekly doses. Our experience with the cladribine-rituximab trial is that patients with significant HCL tumor burden cannot be safely initiated with rituximab without prophylactic steroid.

If successful, this trial could potentially be used in newly diagnosed participants, since the standard of care is single-agent cladribine, which is associated with high CR rate but MRD in 76% of participants, and frequent late relapses. A chemo-free regimen capable of eliminating MRD would be a valuable goal for these participants.

#### 2 ELIGIBILITY ASSESSMENT AND ENROLLMENT

#### 2.1 ELIGIBILITY CRITERIA

#### 2.1.1 Inclusion Criteria

- 2.1.1.1 Diagnosis of HCL or HCLv.
- 2.1.1.2 Treatment required for either 1) Absolute neutrophil count (ANC) <1/nL, 2) Hemoglobin <10g/dL, 3) Platelets<100/nL, 4) symptomatic splenomegaly, or 5) enlarging HCL mass > 2cm in short axis. Participants who have eligible blood counts within 4 weeks from the initiation of study will not be considered ineligible if subsequent blood counts prior to enrollment fluctuate and become ineligible up until the time of enrollment.
- 2.1.1.3 Participants must be Pseudomonas-immunotoxin naïve.
- 2.1.1.4 HCL or HCLv with at least 1 prior purine analog, and, for HCL participants with ≥2-years 1 month response, at least 1 other therapy.
- 2.1.1.5 Age ≥18 years as the disease under study, HCL/HCLv, has not been reported in children < age 18.
- 2.1.1.6 ECOG performance status ≤2 (Karnofsky ≥60%, see **Appendix A: Performance Status** Criteria).
- 2.1.1.7 Participants must have adequate organ and marrow function as defined below:
  - Total bilirubin ≤ 1.5 mg/dL, unless consistent with Gilbert's (ratio between total and direct bilirubin > 5)
  - AST and ALT  $\leq$  3x upper limit of normal (ULN)
  - Alkaline phosphatase < 2.5 ULN
  - Serum creatinine  $\leq 1.5 \text{ mg/dL}$  or creatinine clearance  $\geq 60 \text{ mL/min}$  by Cockcroft-Gault equation, where creatinine clearance = (140 -age)(kg weight)/(72 x Creatinine)
  - Serum albumin > 2 g/dL
  - Partial thromboplastin time (PTT) or Prothrombin time (PT)/International Normalized Ratio < 2.5x ULN (If on warfarin, PT/INR < 3.5x ULN; If on any other anticoagulation, Prothrombin time (PT) < 2.5x baseline)
  - Fibrinogen  $\geq 0.5$  lower limit of normal
- 2.1.1.8 The effects of moxetumomab pasudotox-tdfk and rituximab/Ruxience on the developing human fetus are unknown therefore participants must use effective methods of contraception as directed below.
  - 2.1.1.8.1 Females of childbearing potential (< 50 years) who are sexually active with a non-sterilized male partner must use a highly effective method of contraception prior to study entry and or the duration of study participation and must agree to continue using such precautions for 12 months after completion of rituximab/Ruxience administration. Contraception after this point should be discussed with a responsible physician. Periodic abstinence, the rhythm method, and the withdrawal method are not acceptable methods of contraception. Females of childbearing potential are defined as those who are not surgically sterile (i.e., bilateral tubal ligation, bilateral oophorectomy, or complete hysterectomy) or those who are premenarchal or

Version Date: 04/16/2025

postmenopausal (defined as 12 months with no menses without an alternative medical cause). A highly effective method of contraception is defined as one that results in a low failure rate (i.e., less than 1% per year) when used consistently and correctly. Not all methods of contraception are highly effective. Should a woman become pregnant or suspect she is pregnant while she or her partner is participating in this study, she should inform her treating physician immediately.

- 2.1.1.8.2 Non-sterilized males who are sexually active with a female partner of childbearing potential must use an effective method of contraception from Day 1 until 90 days after receipt of the final dose of investigational product. It is required that a female partner of a male subject also use an effective method of contraception throughout this period.
- 2.1.1.9 Ability of subject to understand and the willingness to sign a written informed consent document.
- 2.1.1.10 Participants must be willing to co-enroll in the investigator's companion protocol 10-C-0066 titled "Collection of Human Samples to Study Hairy Cell and other Leukemias, and to Develop Recombinant Immunotoxins for Cancer Treatment."

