## 2.1.2 Exclusion Criteria

- 2.1.2.1 Participants who have had chemotherapy, immunotherapy or radiotherapy within 4 weeks or treatment with rituximab/Ruxience within last 3 months prior to initiation of treatment.
- 2.1.2.2 Participants who are receiving any other investigational agents.
- 2.1.2.3 Breastfeeding within the projected duration of the study, starting with the screening visit through 6 months after the last dose of rituximab/Ruxience. Pregnant women are excluded from this study because moxetumomab pasudotox-tdfk and rituximab/Ruxience are agents with the potential for teratogenic or abortifacient effects. Because there is an unknown but potential risk for adverse events in nursing infants secondary to treatment of the mother with moxetumomab pasudotox-tdfk and rituximab/Ruxience, breastfeeding should be discontinued if the mother is treated with moxetumomab pasudotox-tdfk and rituximab/Ruxience.
- 2.1.2.4 Participants with known brain metastases should be excluded from this clinical trial because of their poor prognosis and because they often develop progressive neurologic dysfunction that would confound the evaluation of neurologic and other adverse events.
- 2.1.2.5 Uncontrolled intercurrent illness including, but not limited to, ongoing or active infection, symptomatic congestive heart failure, unstable angina pectoris, cardiac arrhythmia, uncontrolled hypertension, uncontrolled pulmonary infection, pulmonary edema or psychiatric illness/social situations that would limit compliance with study requirements.
- 2.1.2.6 Participants with retinal or choroidal detachment.
- 2.1.2.7 Positive for Hepatitis B core antibody or surface antigen unless the participant is on Tenofovir or Entecavir and Hepatitis B Viral deoxyribonucleic acid (DNA) load is <2000 IU/mL
- 2.1.2.8 Active second malignancy requiring treatment other than minor resection of indolent

cancers like basal cell and squamous skin cancers.

- 2.1.2.9 Human immunodeficiency virus (HIV)-positive participants unless taking appropriate anti-HIV medications with a CD4 count of > 200. Otherwise, there may be an increased risk of lethal infections when temporarily suppressing normal B-cells.
- 2.1.2.10 History of an allogeneic bone marrow transplant.
- 2.1.2.11 Participants with a history of both thromboembolism and known congenital hypercoagulable conditions.
- 2.1.2.12 Radioimmunotherapy within 2 years prior to enrollment in the study.

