## 2.2 SCREENING EVALUATION

Screening evaluation testing/procedures are conducted under the separate screening protocol, 01-C-0129 (Eligibility Screening and Tissue Procurement for the NIH Intramural Research Program Clinical Protocols). See also Study Calendar in Section 3.4.

- 2.2.1.1 Laboratory evaluation (needed for eligibility)
  - 2.2.1.1.1 Within 6 months before starting drug, provided >4 weeks after chemotherapy, immunotherapy or radiotherapy prior to entering the study:
  - Bone marrow biopsy (BMBx) with IHC for CD20 and CD3.

Version Date: 04/16/2025

• BMBx is not needed if participants can provide test slides to be read at the Clinical Center along with reports. In case slides and reports are not available, fresh biopsy will be done.

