# 2.2.1.1.4 Within 3 days before starting drug

Pregnancy test (urine or serum). Women of childbearing potential must have a negative pregnancy test

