# 3.4 STUDY CALENDAR

						All cycles  (1 cycle=28 days)					
Procedure	Screen/ Baseline	Pre- Cycle 	Cycle 1 Day -2 	Cycle 1 Day -1 	Days 1-5	Day 8	Day 15±3	EOT 	EOT +	F/U 	Restage 
History & PE	X 	X 						X	6m 		X
Vital signs including pulse oximetry 	$X^3$	$X^{20}$			X 	X		X	Λ		Λ
Performance Score	$X^3$	$X^{20}$			Λ	Λ		Λ			
CBC + Diff	$X^3$	X 	X	X	X	X	X	X	X	X 	X
Weight	X	X	71	71	71	X	21	21	21	71	71
Chemistries  , urinalysis	$X^3$	X 	X 	X 	X	X	X	X	X	X 	X
D-Dimer, Fibrinogen, Ferritin, PT/INR, PTT, amylase, lipase, GGT, IgA, IgG, IgM, CRP, haptoglobin	X 	X 	X 	X 	A	X 	A	X	X	A	X
Reticulocyte count, VWF antigen, VWF activity, PAI-1, FDP, p-selectin, thrombomodulin			X	X							
Cytokine panel 13 			X	X							
Immunofixation electrophoresis (IFE) and TBNK	X	X 				X		X	X		X
Flow cytometry	X 	X 						X	X	X	X
EKG	X 	X 						X	X		X
Lipid panel, TSH, FT4, FT3, T4, T3, SPEP	X 							X	X		X
HBcAB, HBsAg, HIV test	X 										
Pregnancy test (females < 50 years)	X 										
24hr urine protein and creatinine	X 					X 					
NIH Advance Directives Form 	X										
CT Neck-pelvis or MRI 	X 	X						X	X		X
MRI C & T-spine 	X 	X						X	X		X

Version Date: 04/16/2025

Echo, PFTs, stress test, abdominal U/S, HLA	X 										
Adverse Events 	X	X						X			
Concomitant Medications 	X 	X						X	X		
Correlative Studies 		(F	lease refer	to Section I	Error! R	eferen	ce source	not fou	nd.)		
BMBx & BMA w/flow and PCR	X 	X 						X	X		X
Blood PCR	X	X						X 	X 		X 
PaxGene RNA & DNA	X 	X						X	X	X	X
Biomarker	X 	X				X		X	X	X	X
ADAs 	X				X 			X	X 		
PBMCs	X 										
Urine (renal proximal tubule cell		X			X 	X					
damage)		$\Lambda$			Λ	$\Lambda$					
PK and PK bioassay 					X 						

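### The contraception duty stops at age 50 although childbearing potential is defined without an age limit, and the pregnancy-test rules disagree with each other

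*Combined protocol and SAP*

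**What the plan says.** Section 2.1.1.8 opens the contraception criterion by saying that fetal effects are unknown, and "therefore participants must use effective methods of contraception as directed below". The direction for women follows in 2.1.1.8.1: "Females of childbearing potential (< 50 years) who are sexually active with a non-sterilized male partner must use a highly effective method of contraception". The duty begins before study entry and runs until 12 months after the last rituximab/Ruxience dose.

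The same paragraph then defines childbearing potential. The first limb is not being surgically sterile. The sentence continues "or complete hysterectomy) or those who are premenarchal or" and, over the page, "postmenopausal (defined as 12 months with no menses without an alternative medical cause". No age appears in it. Section 2.1.1.5 sets a lower age limit of 18 and no upper limit.

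Section 2.1.2.3 gives the reason for concern: "Pregnant women are excluded from this study because moxetumomab pasudotox-tdfk and rituximab/Ruxience are agents with the potential for teratogenic or abortifacient effects".

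Testing is described in two places:

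- Section 2.2.1.1.4 falls under "Laboratory evaluation (needed for eligibility" and covers the 3 days before drug is started. It says: "Women of childbearing potential must have a negative pregnancy test".
- The study calendar in section 3.4 has the row "Pregnancy test (females < 50 years", marked only in the Screen/Baseline column. Footnote 15 counts the 3 days back from enrollment.

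**The concern.** The age label and the definition select different women, and the text does not say which governs. If the label governs, a participant of 50 or over who still menstruates is of childbearing potential but has no duty to use contraception.

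The other safeguards do not fill that gap. The entry test acts once, at baseline, while treatment may run to 8 cycles. Removal on a positive test (section 3.6.1) and pregnancy reporting (section 8.5.1) act after conception. During treatment and the following 12 months, the contraception duty is the only listed measure that prevents a pregnancy. What is at stake is fetal exposure in a very small number of women.

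The garbled definition matters mainly for the repair. Deleting the age label alone would, on the literal wording, extend the duty to postmenopausal women. The testing mismatch is a consistency error that leaves sites with two rules for one test.

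**Working it through.** The plan states no figure on this point, so the check is a comparison of the rules followed by a rough size.

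**Rules side by side, read literally**

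| Participant | Childbearing potential (definition) | Contraception duty (2.1.1.8.1) | Test under 2.2.1.1.4 | Test under calendar row |
|---|---|---|---|---|
| 50 or over, not sterile, still menstruating | Yes | No | Yes | No |
| Under 50, surgically sterile, still menstruating | No | No | No | Yes |
| 50 or over, not sterile, postmenopausal | Yes on the wording; No on the evident intent | No, only because of the age label | Yes on the wording; No on the evident intent | No |

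The duty column assumes a non-sterilized male partner. The first row is the gap. The second shows the calendar testing more women than section 2.2.1.1.4 below 50. The third shows why the label and the definition must be repaired together.

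Section 2.1.1.8.2, the male clause, refers to a partner of childbearing potential with no age label. So a menstruating partner of 50 is covered, while a menstruating participant of 50 who receives both drugs is not.

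**Timing.** Section 2.2.1.1.4 counts back from the start of drug and footnote 15 from enrollment. One test meets both only if it lies within 3 days of both dates. The documents set no maximum gap between the two.

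**How many women.** Inputs from section 1.2.1 (phase 3 trial): 17 women among 80 patients, median age 60, range 34 to 84. Planned size: 26.

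- Women expected: 17/80 = 21.25%; 0.2125 × 26 = 5.5.
- Under 60, assuming women share the overall median: at most 0.5 × 5.5 = 2.8.
- Affected: assume all women of 60 or over are postmenopausal. Assume also that 0% to 30% of those under 60 are 50 or over, still menstruating, not sterilized and sexually active with a non-sterilized male partner. Then 0 to 0.30 × 2.8 = 0 to 0.8.

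**How long the missing duty lasts.** With one cycle there is a single rituximab/Ruxience dose, so at least 12 months. With 8 undelayed cycles spaced 25 to 28 days:

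- Cycle 1 day -2 to cycle 8 day 1: 3 + 7 × 25 = 178 days to 3 + 7 × 28 = 199 days.
- Adding 365 days: 543 to 564 days, or about 17.8 to 18.5 months. Dosing delays lengthen this.

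**The case against.** The best counter-argument is that an explicit definition normally outranks a bracketed gloss. On that reading the menstruating woman of 50 is covered and the text is merely untidy. This is a fair reading, but it does not remove the conflict: the calendar uses the same under-50 cut-off as a working rule, so a site could reasonably apply the label. If the cut-off was instead a deliberate threshold, the protocol gives no reason for it.

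It can also be said that section 2.1.1.8 imposes a general duty and that the later text only says how to meet it. The clause ties the duty to what follows, so this reading is possible but weak. The consent form and the product labels are not part of the documents reviewed. That nothing restores the duty is therefore true of the visible text only.

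Three further points stand in part:

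- The definition's intended meaning is plain, its literal effect is over-inclusion, and premenarchal status is moot at 18 or over. It is an editorial defect, but it constrains the repair.
- A site that follows section 2.2.1.1.4 closes the testing gap, and pregnant women are excluded at any age. The mismatch is therefore one of consistency.
- The 0% to 30% share has no source in the documents, and a change to an entry criterion helps only future enrollees. Section 3.1.4 records 12 enrolled by 9/24/21, leaving 26 − 12 = 14. On the same assumptions, 0.2125 × 14 = 3.0 women, at most 1.5 under 60, and 0 to 0.45 affected. Accrual at the 04/16/2025 version date is not given, so the number who could still benefit may be zero.

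**Conclusion.** The concern holds as a minor point of participant-safety wording. Followed literally, section 2.1.1.8.1 leaves a still-menstruating participant of 50 or over without a contraception duty, and no other visible section supplies one. The definition sentence is defective, and the calendar departs from section 2.2.1.1.4 on both population and timing.

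The likely reach is 0 to 1 participant. That depends on phase 3 demographics carrying over, on women sharing the overall median age, and on the assumed share, so it is an order of magnitude and not an estimate. For such a woman the missing cover would last at least 12 months, or about 18 months with 8 undelayed cycles. The design, endpoints and analysis are unaffected.

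**What to change.** Make four wording changes in one amendment:

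1. In section 2.1.1.8.1, delete the bracketed age label.
2. In the same edit, reword the definition so that childbearing potential means not surgically sterile and neither premenarchal nor postmenopausal, keeping the existing 12-month criterion for menopause.
3. In the section 3.4 calendar, change the pregnancy-test row to females of childbearing potential.
4. Change footnote 15 to count the 3 days back from the start of drug, matching section 2.2.1.1.4, which stays as it is. It would help to add there which dose is meant, because rituximab/Ruxience is given on day -2 of cycle 1, ahead of moxetumomab pasudotox-tdfk on day 1.

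The amendment needs IRB approval (Statement of Compliance) and could travel with the next planned one. It adds no test beyond what section 2.2.1.1.4 already requires. For about 0 to 1 woman it adds the contraception duty that younger women already carry.
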